2 STUDY ENDPOINTS

2.1 PRIMARY EFFICACY ENDPOINT

- (i) To determine whether posterior left atrial wall (PLAW) isolation in conjunction with pulmonary vein isolation (PVI), as compared to PVI alone, can yield a reduction in atrial arrhythmia recurrence at 1 year in patients with persistent/long-standing persistent atrial fibrillation (AFp) undergoing catheter ablation therapy

2.2 PRIMARY SAFETY ENDPOINT

- (i) To evaluate the overall complication rate associated with PLAW isolation in conjunction with PVI as compared to PVI alone, in patients with AFp undergoing catheter ablation therapy

3 INTRODUCTION, RATIONALE AND OBJECTIVE

Catheter ablation has emerged as a safe, practical and effective strategy for treatment of atrial fibrillation (AF), with pulmonary vein isolation (PVI) as the primary cornerstone of this strategy. On the other hand, the success rate associated with catheter ablation of persistent/long-standing persistent AF (AFp) remains significantly lower than that of paroxysmal AF, with wide variations in the ablation technique among different operators¹. To date, several studies have prospectively examined the impact of substrate (complex fractionated electrogram) and linear ablation^{2,3,4}. Yet, none of these studies have found a clear benefit associated with either approach over PVI, alone. Meanwhile, some investigators contend that the mechanism for maintenance of AFp may be inherently different from that of paroxysmal AF, implicating the posterior left atrial wall (PLAW) as a potential culprit⁵. Along these lines, Corradi et al.⁶ discovered an increased incidence of PLAW structural remodeling using light microscopy in patients with as opposed to those without AFp. Similarly, Cutler et al.⁵ found that the presence of PLAW scar served as an important ablation target in patients with AFp.

The PLAW implication in patients with AFp is in fact plausible, as this structure shares its embryological origins with the primordial pulmonary veins⁷. As such, a number of studies and published reports have previously described the presence of rotors and spontaneous triggers within the PLAW^{8,9,10}. Moreover, several small-sized and/or single-center studies have illustrated the feasibility^{11,12,13} and even the potential benefit^{14,15,16,17} associated with electrical isolation of the PLAW in conjunction to PVI in AFp patients undergoing catheter ablation therapy. However, presently there is a paucity of randomized-controlled data to address the role for such an approach. Thus, the aim of this multicenter, randomized-controlled trial is to prospectively compare and analyze the approach of PVI with or without PLAW isolation in a large cohort of patients with symptomatic AFp.

4 STUDY DESIGN

Patients with symptomatic AFp undergoing catheter ablation of AF will be randomized to either PVI alone (Group 1) or PVI + PLAW isolation (Group 2).

5 STUDY SUBJECTS

5.1 INCLUSION CRITERIA

In total, 200 patients with symptomatic AFp will be enrolled in this multicenter, randomized, prospective, single-blinded study. Consistent with the current definitions¹⁸, all patients with persistent AF must have ≥ 1 documented episode of AF lasting >1 week in duration or lasting <7 days but requiring electrical/pharmacological cardioversion to sinus rhythm. Patients with long-lasting persistent AF will be defined as those with continuous AF of >1 year duration.

- Males and females with an age >18 years undergoing a first-time catheter ablation of AF; prior ablation of a right atrial cardiac arrhythmia (i.e., typical right atrial flutter) is permitted
- All patients must understand the requirements of the study and be willing to comply with the post-study follow-up requirements
- Patients must be in AF on the day of the procedure

5.2 EXCLUSION CRITERIA

- Any reversible cause of AF (post-operative, thyroid disorder, etc)
- Patients with cerebral ischemic events (stroke or transient ischemic attack), myocardial infarction or unstable angina in the previous 2 months
- Patients with complex congenital heart disease
- Patients with a history of hypertrophic cardiomyopathy
- Patients with cardiomyopathy and a left ventricular ejection fraction $<35\%$
- Congestive heart failure, class IV
- Women who are known to be pregnant or have had a positive β -HCG test 7 days prior to procedure

- Patients whose life expectancy is <1 year
- History of left-sided left atrial ablation (catheter or surgically-based)
- Mental impairment precluding the patient from providing informed consent or completing appropriate follow-up

6 SAMPLE SIZE

We plan to enroll 200 patients in this multicenter, prospective, randomized single-blinded trial. Of these, 100 patients will be assigned the arm receiving PVI (Group 1) and 100 patients to the arm receiving PVI + PLAW isolation (Group 2). However, an interim analysis will be performed after enrolling the first 100 patients (50 patients in each arm) to assess for the primary efficacy and safety endpoints. Decisions regarding further enrollment will be made accordingly based on this interim analysis.

7 PATIENT ENROLLMENT AND WITHDRAWAL

Patients meeting the study inclusion criteria will be identified in the outpatient setting by one of the study sites primary or co-investigators. The study will be thoroughly described during the initial clinic visit including the potential risks and benefits. Consent will typically be obtained at the time of the initial assessment if it is clear that the patient understands the nature of the study. Alternatively, the patient will be allowed to take a copy of the consent form home to contemplate whether they would like to be enrolled in the study. A sample consent form can be found in Appendix 1. Only patients who voluntarily provide consent will be included in this study.

Of note, randomization is performed prior to the ablation procedure. Consent will be obtained prior to undergoing the ablation. Patients will be able to withdraw from the study at any point without compromising their medical care. We expect to achieve $\geq 90\%$ rate of follow-up.

8 STUDY PROCEDURE

This study will evaluate a standardized approach of PVI to PVI + PLAW isolation.

8.1 PRE-PROCEDURAL EVALUATION

The following tests and procedures will occur before the ablation:

- Recording of patient medical history (including CHA2DS2-VASc score, duration of AF, number of cardioversions)
- Recording medication history (history of antiarrhythmic drugs [AADs], duration of AAD use)
- Symptom assessment using the CCS-SAF score (19) (Appendix 2).
- CT or MRI scan within six (6) months of the procedure is recommended
- Echocardiogram (preferably a transthoracic study with complete measurement of cardiac dimensions and left atrial assessment) within 1 year of the procedure
- β -HCG in women of child bearing age on the morning of the procedure

8.2 PRE-PROCEDURAL MEDICATION MANAGEMENT

- Therapeutic anticoagulation is recommended for 3 weeks prior to the procedure (if not possible, intra-procedure transesophageal or intracardiac echocardiography is recommended to exclude a left atrial thrombus)
- All AADs except amiodarone will be discontinued at least 5 half-lives prior to the procedure; amiodarone may be continued throughout the peri-procedural period

9 ABLATION DETAILS

- Patients will be taken to the electrophysiology laboratory in a fasting state
- All patients must be in AF at the start of the procedure
- General anesthesia or conscious sedation will be used at the discretion of the primary electrophysiologist
- Esophageal temperature monitoring is highly recommended

- Vascular access, number of transseptal punctures and catheter selection will be left to the discretion of the operator
- All cases will be performed utilizing 3-dimensional electro-anatomical mapping with St. Jude NavX (St. Jude Medical, Inc, St. Paul, MN)
- A post-ablation voltage map is recommended
- Circumferential PVI must be performed first
- Bi-directional block must be demonstrated following PVI before and after a drug challenge (isoproterenol or adenosine)
- Radiofrequency ablation must be performed using an irrigated-tip ablation (TactiCath or FlexAbility ablation catheters, St. Jude Medical, Inc)
- Cardioversion to ensure PVI is permitted
- Ablation of other arrhythmias inducible at the time of ablation (i.e., right- or left-sided atrial flutters) is permitted

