10 RANDOMIZATION AND STUDY SITES

- Patients will be randomized prior to the procedure to either PVI (Group 1) or PVI + PLAW isolation (Group 2)
- However, the operator will be blinded to this until the completion of PVI
- Once bilateral PVI has been completed, the operator will be notified by his/her research coordinator as to whether the patient will undergo PLAW isolation
- Numbering of the subjects when completing all case report forms (CRFs):

1 - 2 - 3 - 4

1: Site number (each site will be assigned a unique number)

2/3/4: Overall patient number (001 – 200)

- Site participating in this clinical trial include:
 - 1) Mercy General Hospital and Dignity Health Heart & Vascular Institute, Sacramento, CA, USA
 - 2) Instituto de Pesquisa em Arritmia Cardiaca, Hospital Cardiologico, Florianopolis SC, Brazil
 - 3) Center for Atrial Fibrillation, Hospital Pró-Cardíaco, Rio de Janeiro, Brazil

4) Sunnybrook Health Sciences Centre, University of Toronto, Toronto, ON, Canada

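### Allocation is disclosed once PVI is complete, and nothing requires the choice of other ablation targets to be made before then, so those discretionary lesions may be chosen with the arm known

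*Protocol*

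**What the plan says.** Three rules bear on the point, all in the protocol.

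- **Order of ablation (section 9):** "Circumferential PVI must be performed first".
- **Masking of the operator (section 10):** patients are randomised before the procedure. "However, the operator will be blinded to this until the completion of PVI". Then: "Once bilateral PVI has been completed, the operator will be notified by his/her research coordinator as to whether the patient will undergo PLAW isolation".
- **Additional ablation (section 9):** "Ablation of other arrhythmias inducible at the time of ablation (i.e., right- or left-sided atrial flutters) is permitted". The permission is the same in both groups. Section 9 gives no timing for it relative to disclosure, no induction procedure and no limit on the lesions.

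Section 9 also requires block to be shown after PVI, both before and after a drug challenge. It does not say whether this check comes before or after the coordinator's message. Section 11.4 names atrial flutter alongside AF as a recurrence. Section 6 describes the trial as single-blinded, with 100 patients per group.

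**The concern.** The sponsor took the trouble to conceal the arm during PVI, which protects the component that both groups share. The concealment can end just before a step that leaves much more to judgement, namely whether to look for and treat other arrhythmias, and with which lesions. An operator who knows that a patient will have PVI alone may look harder or treat more readily. An operator who knows that posterior wall isolation is to follow may do less, or may add other left atrial lesions while working there.

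Flutter is part of the recurrence endpoint, so these lesions can act on the primary outcome directly. An excess in Group 1 would shrink the contrast, and an excess in Group 2 would credit posterior wall isolation with the effect of something else. No later analysis can restore concealment once the arm has been disclosed, so this belongs in the protocol and cannot be left to the SAP.

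**Working it through.** **Step 1: the sequence.** Section 9 places PVI before any other ablation. Section 10 ends the masking at completion of PVI. Other ablation therefore follows PVI, and disclosure may precede it. What is not fixed is when PVI counts as complete (before or after the drug challenge) and when other arrhythmias are identified. A short masked interval after PVI is possible, but nothing requires it or requires a decision to be recorded in it.

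**Step 2: is there a plan figure to reproduce?** No. Section 6 gives 200 patients without significance level, power, recurrence rates or effect size. The size can only be illustrated with assumed inputs.

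**Step 3: dilution, if the excess is in Group 1.**

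Inputs:
- n = 100 per arm (section 6).
- Two-sided 0.05 (assumed).
- Recurrence p1 = 0.40 and p2 = 0.218 (assumed; chosen because they give 80% power at 100 per arm).
- f = share of Group 1 given extra ablation only because the arm was known (assumed).
- g = fraction of the Group 2 benefit that those patients gain (assumed).

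Formulas:
- Diluted Group 1 rate: q = p1 − f·g·(p1 − p2).
- Power ≈ Φ[(d − 1.96·SE0)/SE1], with d = q − p2, SE0 = √(2·p̄(1 − p̄)/n), p̄ = (q + p2)/2 and SE1 = √(q(1 − q)/n + p2(1 − p2)/n).

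With no dilution, d = 0.182, SE0 = 0.0653 and SE1 = 0.0641. Power is Φ[(0.182 − 1.96 × 0.0653)/0.0641] = 80.0%.

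| f | g | q | Difference (points) | Power |
|---|---|---|---|---|
| 0 | – | 0.400 | 18.2 | 80.0% |
| 5% | 1 | 0.391 | 17.3 | 76.1% |
| 10% | 1/2 | 0.391 | 17.3 | 76.1% |
| 10% | 1 | 0.382 | 16.4 | 71.8% |

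The second and third rows agree because only the product f·g matters.

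Other assumed rates show the same pattern. For f·g of 0, 5% and 10%, power is 83%, 79% and 75% at 50% v 30%, and 62%, 58% and 54% at 40% v 25%.

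**Step 4: false signal, if posterior wall isolation has no effect.** Suppose one arm has an arm-driven excess s of patients given extra ablation, which lowers their recurrence by b points. The arms then differ by s·b. With s from 10% to 30% and b from 10 to 20 points (all assumed), the difference runs from 0.10 × 10 = 1 point to 0.30 × 20 = 6 points. At a base rate of 40% or 50% and 100 per arm, the two-sided rejection rate rises from 5% to between about 5.2% and 14%. Small imbalances hardly matter; large ones do.

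**The case against.** Several points on the other side stand.

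- **Masking cannot last.** The operator who isolates the posterior wall must know the arm, and single-blinding is declared. This is an improvement to a workable rule. It corrects no contradiction.
- **The permission is symmetric.** It covers both arms and is confined to inducible arrhythmias. A patient with a truly inducible flutter may well be ablated whether or not the operator knows the arm. That ablation is not attributable to the timing of the disclosure, and moving the disclosure would recover none of it.
- **Extra lesions may do little.** Section 3 reports that earlier studies of substrate and linear ablation showed no clear gain over PVI alone. Flutter lines are not posterior wall isolation, and right-sided ablation does not touch that wall. Full transfer of the Group 2 benefit (g = 1) is therefore a severe assumption.
- **Some arrhythmias come late.** Patients must start the procedure in AF, so a flutter may show itself only later, and some may appear only after posterior wall lesions. A log made before disclosure cannot cover these.

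A reader might infer that every discretionary left atrial lesion is chosen with the arm known. The protocol does not say so, because the order of the drug challenge, the search for other arrhythmias and the coordinator's message is left open. A reader might also charge all additional ablation in Group 1 to the disclosure and infer a larger power loss. Only the excess caused by knowing the arm can be charged to it, and the protocol gives nothing from which to estimate that excess or its direction.

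None of this removes the gap: the decision may be made with the arm known, and part of that is avoidable.

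**Conclusion.** The point holds as a minor, avoidable risk of performance bias. The protocol allows discretionary ablation that bears on the primary endpoint to be chosen after the operator learns the arm, and it requires no earlier decision. Both size and sign are unknown: the net effect could be dilution or inflation.

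The illustrations in the working put the loss at roughly 4 points of power for a 5% arm-driven excess in Group 1 with full benefit, or for 10% with half the benefit, and at about 8 points for 10% with full benefit. They rest on assumed recurrence rates, an assumed two-sided 0.05 test and an assumed excess. Only the 100 per arm comes from the protocol, so they show scale and do not predict this trial's power.

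**What to change.** In section 10, state that the coordinator discloses the arm only after two things have happened: PVI block has been confirmed before and after the drug challenge, and the operator has logged any other arrhythmias already seen and intended for ablation. Add a CRF item that flags any lesion added after disclosure.

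This moves the moment of disclosure and nothing else. Operator discretion is unchanged, and no new induction step is mandated.

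The cost is one sentence in section 10, one CRF item and a short delay before disclosure. Arrhythmias that appear only later, for example after posterior wall isolation, cannot be covered by the log, but flagging will make any imbalance between the arms visible.

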10 RANDOMIZATION AND STUDY SITES

- Patients will be randomized prior to the procedure to either PVI (Group 1) or PVI + PLAW isolation (Group 2)
- However, the operator will be blinded to this until the completion of PVI
- Once bilateral PVI has been completed, the operator will be notified by his/her research coordinator as to whether the patient will undergo PLAW isolation
- Numbering of the subjects when completing all case report forms (CRFs):

1 - 2 - 3 - 4

1: Site number (each site will be assigned a unique number)

2/3/4: Overall patient number (001 – 200)

- Site participating in this clinical trial include:
 - 1) Mercy General Hospital and Dignity Health Heart & Vascular Institute, Sacramento, CA, USA
 - 2) Instituto de Pesquisa em Arritmia Cardiaca, Hospital Cardiologico, Florianopolis SC, Brazil
 - 3) Center for Atrial Fibrillation, Hospital Pró-Cardíaco, Rio de Janeiro, Brazil

4) Sunnybrook Health Sciences Centre, University of Toronto, Toronto, ON, Canada

11 POST-PROCEDURAL MANAGEMENT

11.1 POST-PROCEDURAL FOLLOW-UP

- All patients will be monitored for a minimum of 6 hours and will typically be discharged either on the day of the procedure or the following day
- Complications (i.e., vascular, bleeding, stroke, etc) will be documented
- Patients will be instructed to call the local study coordinator or his/her cardiac electrophysiologist with any questions or concerns during the follow-up period

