12 SAFETY

As the components of this study are all within the realm of usual clinical care and common clinical practice, we do not anticipate any incremental adverse events. Patients will report symptoms/adverse events to their local site study coordinator and primary cardiac electrophysiologist during the follow-up period. The local site primary investigator will oversee the safety of the study at his/her site. All adverse events will be reported to the Principal Investigators (Drs. [name] and [name]). Adverse events will be monitored and tallied for each 10 patients enrolled in the study.

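### After discharge, complications for the primary safety endpoint are found by patient-initiated reporting, with no scheduled inquiry, so late events are likely to be under-captured

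*Protocol*

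**What the plan says.** Protocol section 2.2 makes complications a primary endpoint: "To evaluate the overall complication rate associated with PLAW isolation in conjunction with PVI as compared to PVI alone".

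Three places describe how complications come to light:

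- **Around the procedure (section 11.1).** Observation lasts at least 6 hours, and patients usually go home the same day or the next. A separate item adds: "Complications (i.e., vascular, bleeding, stroke, etc) will be documented".
- **After discharge (sections 11.1 and 12).** Section 11.1 states: "Patients will be instructed to call the local study coordinator or his/her cardiac electrophysiologist with any questions or concerns". Section 12 repeats the rule: "Patients will report symptoms/adverse events to their local site study coordinator and primary cardiac electrophysiologist during the follow-up period". Events then go to the principal investigators, and "Adverse events will be monitored and tallied for each 10 patients enrolled in the study".
- **Scheduled testing (section 11.2).** Ambulatory ECG recording at 3, 6 and 13 months, from which patients with an existing CIED are exempt, and a recommended echocardiogram at 4–6 months to look at left atrial size. Neither is linked to collecting complications.

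Section 13 lists the risks. Some arise during the procedure or the hours after it. Others, such as pulmonary venous stenosis, esophageal injury and pneumonia, can show themselves after the patient has gone home.

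**The concern.** A primary endpoint should be looked for in the same way, at the same times, in every patient. Here the efficacy endpoint has scheduled recordings, while the safety endpoint, once the patient leaves hospital, has an instruction to the patient. A patient who does not connect a symptom with the ablation, or who is treated elsewhere, may never report it.

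Two consequences follow. If late events are missed equally in both arms, both observed rates fall, the difference between them shrinks and the comparison loses sensitivity. That matters because Group 2 receives additional ablation of the posterior wall, and section 12 starts from the expectation of no incremental adverse events; passive collection tests that expectation weakly. The interim analysis after 100 patients (section 6) also assesses safety and informs further enrollment.

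If late events are not recorded equally, the difference itself is biased. Under section 10 the research coordinator tells the operator the arm once pulmonary vein isolation is complete, and under sections 11.1 and 12 the coordinator and the electrophysiologist receive the patients' reports. How far they follow up a vague complaint could depend on knowing the arm.

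**Working it through.** **Reading the text.** Each provision in turn, asking whether it finds events or handles events already known:

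| Provision | Finds late events? |
|---|---|
| Monitoring for at least 6 hours (11.1) | No; it ends at discharge |
| Complications documented (11.1) | Records known events; no method or schedule for finding them |
| Patients told to call (11.1), patients report (12) | Yes, if the patient takes the initiative |
| Tally per 10 patients enrolled (12) | Counts events already reported |
| ECG recordings at 3, 6 and 13 months (11.2) | Only incidentally; no complication question; CIED patients exempt |
| Echocardiogram at 4–6 months (11.2) | Only incidentally; recommended, for atrial size |

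Patient-initiated reporting is the only route that the protocol states for events after discharge.

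**Size, as an illustration.** The protocol gives no complication rate, capture rate, significance level or power, so there is no figure to reproduce. From the document: 100 patients per arm (section 6). Assumed: true rates of 4% v 12%; a late share f of 20–50% of events; a captured share c of 60–80% of late events, equal in both arms; two-sided exact Fisher test at 5%.

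Observed rate = true rate × (1 − f + f·c). Only late events are thinned; events before discharge are fully counted.

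| f | c | Factor | Observed rates | Fisher power |
|---|---|---|---|---|
| – | 100% | 1.00 | 4.0% v 12.0% | 46.5% |
| 20% | 80% | 0.96 | 3.84% v 11.52% | 44.5% |
| 20% | 60% | 0.92 | 3.68% v 11.04% | 42.4% |
| 30% | 80% | 0.94 | 3.76% v 11.28% | 43.4% |
| 30% | 60% | 0.88 | 3.52% v 10.56% | 40.2% |
| 50% | 80% | 0.90 | 3.60% v 10.80% | 41.3% |
| 50% | 60% | 0.80 | 3.20% v 9.60% | 35.6% |

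Power falls from about 47% to about 36–44%.

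**A rare late event.** With an assumed true risk of 1% in an arm of 100, the chance of seeing at least one case is 1 − 0.99^100 = 63% with full capture. It is 1 − 0.992^100 = 55% at 80% capture and 1 − 0.994^100 = 45% at 60%.

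**Unequal recording.** Assume the same true rate of 10% in both arms, f = 30%, and capture of late events of 90% in one arm and 70% in the other. The observed rates are 10% × (0.7 + 0.3 × 0.9) = 9.7% and 10% × (0.7 + 0.3 × 0.7) = 9.1%, a spurious difference of 0.6 percentage points.

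**The case against.** The strongest replies are these.

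- **Much of this is silence.** The protocol does not say that complications will not be asked about at the scheduled recordings, and the case report forms, which are not shown, may carry a checklist. That is possible. But sections 11.1 and 12 do state how events reach the site, and that rule depends on the patient. An analysis plan cannot recover events that nobody asked about.
- **The counting window belongs in the SAP.** This stands. The absence of a window for the complication rate is not a fault by itself, because an SAP may supply it. It enters only as part of the fix.
- **Phoning is not the only route.** This stands. Patients may report to the electrophysiologist at any contact, and recordings or echocardiograms may bring events to light. A reader might infer that late complications will certainly be missed and that the whole endpoint hangs on telephone calls. The documents do not support that: they give no capture rate, and events before discharge do not depend on a call.
- **The loss of power is modest.** This stands. Thinning all events by 20% or 40% would take power from 46.5% to 35.6% or 23.3%, but the heavier loss requires 40% of all complications to go unseen, including those during the procedure. Nothing in the protocol supports that. Even with full capture, power is below 50% under the assumed rates, so the limit comes mainly from the sample size.
- **Bias between arms is speculative.** Largely so. The trial is single-blinded without naming the blinded party; if it is the patient, self-reports should differ little by arm. A reader might infer that the plan will produce a false safety signal. Even 90% v 70% capture applied to every event at a true 10% (9% v 7% observed) gives a significant Fisher result only 4.8% of the time. What remains is a possible distortion at the point where unblinded staff follow up and record.

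**Conclusion.** The point holds in a measured form. For a primary endpoint, the protocol's stated means of finding complications after discharge is patient-initiated reporting, and nothing else in it adds active inquiry. Late complications are therefore likely to be under-captured, which makes the arm comparison less sensitive; uneven recording by unblinded staff is possible but not shown.

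The size cannot be derived from the documents. The fall in Fisher power from 47% to about 36–44% rests entirely on the assumed rates of 4% v 12%, a late share of 20–50% and capture of 60–80%. It shows the direction and the rough order of the loss and is not an estimate for this trial. The change is worth making because it is cheap and must be in place while patients are being followed.

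**What to change.** In sections 11.1 and 12, add that every patient in both arms is asked the same scripted checklist of the section 13 events, with onset dates, at discharge and at the 3-, 6- and 13-month contacts. CIED patients who have no recording need a short call at the same times; otherwise the checklist would not reach them. Where feasible, the questions should be put by existing staff who do not know the arm, since a script alone does not remove the influence of an unblinded coordinator. Patient-initiated reports continue alongside.

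Count the primary safety endpoint from the procedure over the same fixed period in both arms. No contact falls between discharge and 3 months, so any 30-day count would come from the onset dates collected at the 3-month contact.

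The cost is a one-page form, a few minutes per contact, brief calls to CIED patients, and some recall error for early events.
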